4.3 ASSESSMENT AND MANAGEMENT OF RISK

This is a low risk study, and is categorised as a study limited to working with human tissue samples and/or analysis of data. There will be no research specific participant contact or observation and therefore no AEs/SAEs would occur because of study participation.

4.4 STUDY PROCEDURES

Please refer to the flow chart on page viii for a summary of the study procedures. The study procedures described below will be conducted in accordance with SOPs and/or work instructions provided by the CI.

4.5 STUDY INTRODUCTION

This study seeks to gain consent from patients remotely via the telephone. Samples will be scavenged from routine care samples (no additional procedures will occur i.e. blood draws etc.). The study is being designed to limit the burden on clinical staff. The NHS is currently facing massive pressures and unprecedented demand. However, we should continue to seek improvement this study has been designed so we can continue to improve our services while putting minimum burden on the Oncology staff. This project is part of a service improvement project to highlight which blood tests are best at predicting irAEs.

4.6 STUDY OPT OUT

Patients that have been recruited on the study will have their NHS numbers extracted into a list. Once a month before running of the sample batches, this list of NHS numbers will be raised on the Trust's internal system called Mycall <http://MyCall> as a National Data Opt out. Any patients who have opted out of having their data and records used for research will be removed from the study

BIO-CHECKPOINT

and the samples destroyed as in line with local pathology procedures. This is in line with local trust policy that has been created to ensure compliance with the NHS National Data Opt-out policy.

4.7 STAFF TRAINING

Information about the study training will be provided by the research team. Local in house training procedures will be followed for the operation of the analysers. [name] will receive additional research based training as part of her Doctorate with the University of Manchester. [name] has also completed Good Clinical Practice basic research training.

5.0 SAMPLE PROCESSING

5.1 SAMPLE COLLECTION AND STORAGE

Patients will be identified via the chemotherapy scheduling system, which will be reviewed and checked by lead researcher [name] daily Monday-Friday. Patients who are yet to start ICPI will be listed in a password protected sheet with the expected day of their chemo. The lead researcher will then check to assess that if the patients listed meet the inclusion criteria and if they have any of the features of the exclusion criteria. Those that meet the exclusion criteria will be deleted off the list. The laboratory information management system will be reviewed daily to assess if we have received their clinical bloods. Left over serum and plasma will be stored frozen and tested in batches once a month.

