2.0 BACKGROUND

This study aims to identify biomarkers that stratify Oncology patients on immune check point inhibitor (ICPI) that have an increased risk of developing autoimmune toxicity known as immune-related adverse events (irAE).

ICPIs are being increasingly prescribed and 10% of NHS Oncology patients receive treatment from this drug group (1,2). The reported rate of total irAE triggered by ICPI varies but is thought to be between 40-66% (3-5), a third of which are endocrine related (6,7).

Several bodies including the European Society for Medical Oncology, American Society for Clinical Oncology and the National Comprehensive Cancer Network have produced guidance for irAE management, but no unified screening protocol exists to stratify patients at high-risk (8). Currently the literature primarily centres around looking for prognostic biomarkers for treatment success rather than characterising toxicity.

Individual studies review the utilisation of some routine clinical blood tests, i.e., albumin, rheumatoid factor, lactate dehydrogenase, IL-6, etc, to screen and stratify high-risk patients (9,10). However, these tests are used in isolation and no singular clinical algorithm using a variety of routine tests has been developed for initial screening during ICPI therapy. A variety of protocols have been developed for screening endocrine irAE, although these are not consistently adopted, and practice varies.

ICPIs induce an enhanced immunological response to promote anti-tumour activity (11). There are a few forms of ICPI including CTLA-4 antibodies that upregulate T-cell activation pathways to enhance the tumour immune response. There are also antibodies that act as programmed death receptor agonists, which promote cytokine release and T-cell activation. (12)

An array of studies has shown that reactive oxygen species (ROS) are involved in the regulation of T-cell anti-tumour immunity (13–20). ICPI are active therapies that alter T-cell intracellular signalling, which can increase ROS production and proinflammatory cytokine secretion, thus exerting an immunotherapeutic effect (13).

irAE refers to a spectrum of autoimmune toxicities triggered by ICPI. ROS are implicated in the initiation, amplification, pathogenesis of autoimmune diseases (21,22). Are ROS heavily upregulated in irAE due to a dysregulated immune response and could the measurement of an oxidative stress marker act as a marker of toxicity?

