Malondialdehyde is generated from ROS driven lipid peroxidation of polyunsaturated fatty acids and is an indirect marker of oxidative stress. Malondialdehyde can be detected within plasma, serum and urine via liquid-chromatography mass-spectrometry (LC-MS/MS). (23–25) Malondialdehyde has been suggested as a future marker of tissue level thyroid dysfunction, the most common irAE is hypothyroidism (26).

BIO-CHECKPOINT

At present, Portsmouth does not have a unified screening process for patients about to commence ICPI and tests requested are clinician dependent. This project seeks to produce a unified clinical algorithm.

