3.2 Secondary objectives

This principal research question will be broken down to the following sub aims:

1. Are there any established biochemistry, haematology and immunology blood tests that produce significantly different results in those who develop irAE when compared to those that don't. Including IL-6 (requires in-house verification). Observational study
2. Can a malondialdehyde LC-MS/MS assay suitable for clinical laboratory use be developed based on a method development by Sobsey *et al.*
3. Is malondialdehyde significantly raised in those who develop irAEs compared to those that do not. An ELISA kit has been located in the event an LC-MS/MS method is not successfully developed.
4. Can a blood test clinical algorithm be developed to stratify patients at high-risk of developing an irAE.

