3.3 Outcome

This project could produce a clinical algorithm and/or blood test panel that successfully highlights patients at a high risk of developing irAE, prior to commencing therapy. This would allow closer monitoring of high-risk patients, leading to earlier diagnosis of irAE. Currently irAE can be tricky to diagnose and have overlapping symptoms with the malignancy and related concomitant treatments (27). Earlier diagnosis would lead to reduced hospitalisation, better outcomes, and reduced

BIO-CHECKPOINT

interruptions to the anti-cancer therapy, which may lead to better malignancy curative rates. There is also a potential to reduce morbidity and mortality risk for this subset of patients, as well as an overall reduction in resource burden.

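### Does an implied pre-dose sample leave the malondialdehyde objective unable to test its own rationale?

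*Combined protocol and SAP*

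**What the plan says.** On when the sample is taken, three places point to the period before treatment. Section 5.1: "Patients who are yet to start ICPI will be listed in a password protected sheet with the expected day of their chemo", after which the laboratory system is checked daily for those patients' routine bloods. Section 2.0, on the local problem: "Portsmouth does not have a unified screening process for patients about to commence ICPI". Section 3.3, on the intended product: a panel or algorithm that "highlights patients at a high risk of developing irAE, prior to commencing therapy". No draw window or cut-off relative to the first dose is given. The lay summary (section 1.0) and one sentence of section 2.0 describe patients or screening on treatment, which leaves the timing a little open. Section 4.4 refers to a flow chart that cannot be read in the available text and may settle it.

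On what is compared, item 3 of section 3.2 asks: "Is malondialdehyde significantly raised in those who develop irAEs compared to those that do not". It gives no time point.

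On why malondialdehyde, section 2.0 offers four reasons:

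- a drug effect: "ICPI are active therapies that alter T-cell intracellular signalling, which can increase ROS production and proinflammatory cytokine secretion";
- a role in autoimmunity: "ROS are implicated in the initiation, amplification, pathogenesis of autoimmune diseases";
- a state during the event: "Are ROS heavily upregulated in irAE due to a dysregulated immune response";
- a thyroid link: "Malondialdehyde has been suggested as a future marker of tissue level thyroid dysfunction, the most common irAE is hypothyroidism".

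**The concern.** The sample and the argument for the marker seem to belong to different times. Before the first dose the drug cannot yet have raised oxidative stress and no irAE exists. Section 4.2 also excludes patients with a history of autoimmune or endocrine disease, so recognised disease of that kind should be absent at baseline. Of the four reasons, only the one on the initiation of autoimmune disease clearly fits a baseline sample.

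The risk is over-reading in both directions. A null result could be reported as evidence that malondialdehyde does not rise with irAE, when the blood was drawn before any rise could occur. A positive result could be reported as support for a treatment-driven mechanism that was never observed. Leftover material is destroyed after testing (sections 4.1 and 5.3), so a later sample could not be added afterwards from stored stock.

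**Working it through.** **Which question each passage poses**

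| Place | Question | Sample time that answers it |
|---|---|---|
| 3.3 | Who is at high risk before therapy? | Pre-dose |
| 3.2 item 3 | Is malondialdehyde higher in those who go on to an irAE? | Not stated; pre-dose fits 3.3 |
| 2.0, drug effect | Does ICPI raise oxidative stress? | After exposure |
| 2.0, autoimmunity | Are reactive oxygen species involved in initiating autoimmunity? | Pre-dose or later |
| 2.0, during irAE | Are they raised in the irAE? | At the event |
| 2.0, thyroid | Does malondialdehyde mark thyroid dysfunction? | Mainly at the event |

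The mismatch lies between the background and the sample. The objective and its intended use agree with the sample.

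**How far a pre-dose sample dilutes a later difference**

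Inputs from section 7.0: about 120 patients expected, a stated minimum of 47, irAE incidence 40%. Hence 0.40 × 120 = 48 against 72, and 0.40 × 47 ≈ 19 against 28. Assumed, because the plan gives no values: a later difference d in SD units, a share f of it already present before the dose, and a two-sided t-test at 0.05 (the plan names no test).

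Noncentrality = f·d / √(1/n₁ + 1/n₂). For 48 against 72, √(1/48 + 1/72) = 0.1863. With d = 0.6:

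- f = 1: 0.6/0.1863 = 3.22, power 89%
- f = 0.5: 0.3/0.1863 = 1.61, power 36%
- f = 0.25: 0.15/0.1863 = 0.805, power 13%
- f = 0: noncentrality 0, rejection rate 5%

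| Patients | d | f = 0 | 0.25 | 0.5 | 1 |
|---|---|---|---|---|---|
| 48 v 72 | 0.6 | 5% | 13% | 36% | 89% |
| 48 v 72 | 0.8 | 5% | 19% | 57% | 99% |
| 19 v 28 | 0.6 | 5% | 8% | 17% | 51% |

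The f = 0 column is simply alpha. The other columns show that a smaller difference has less power. They describe the chance of detecting a later rise. They are not a loss for prediction, because a difference absent before the dose cannot help a pre-dose algorithm.

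**Whether the unwritten window threatens the prediction analysis**

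Suppose 2% of irAE patients' samples were in fact drawn at onset, with a shift of 1 or 2 SD. The group mean moves by 0.02 × 1 = 0.02 SD or 0.02 × 2 = 0.04 SD. Simulated at 48 against 72, the false-positive rate is 5.2 to 5.3% and 5.6%.

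If instead patients without a pre-dose sample are left out, the difference detectable with 80% power rises from 0.53 SD at N = 120 to 0.54, 0.56 or 0.59 SD when 5, 10 or 20% are lost (N = 114, 108, 96).

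**Whether a later sample would repair the match**

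The natural remedy is one further leftover sample at a fixed on-treatment visit, compared among patients still free of irAE. With d = 0.6, power is 89% for 48 against 72, 84% if 20% of irAEs come earlier (38 against 72), and 75% if 20% of patients also lack leftover material (30 against 58). These figures assume that the whole 0.6 SD is present before the irAE appears. If only half is, the same formula gives noncentralities of 1.61, 1.50 and 1.33, and power of 36, 32 and 26%. Restricting to irAE-free patients also removes the at-event state, on which two of the three later-time reasons rest.

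**The plan's own figure**

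The minimum of 47 cannot be reproduced, because section 7.0 gives no effect size or test. Nothing above depends on how it was obtained.

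**The case for a change.** The strongest case for a change is that it costs little and cannot be made later. Writing the sampling window into section 5.1 and the word pre-treatment into item 3 of section 3.2 would take a few lines. The de-identified analysis sheet described in section 4.1 lists no sample date, so the file as described would not show that a sample came before the dose. Leftover samples will be gone by the time anyone asks. A new mass-spectrometry assay is also being set up, so misreading its first clinical result would matter.

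Part of this stands. The window is not written down, the on-treatment wording in sections 1.0 and 2.0 does not help, and a sample-to-dose interval would be useful in the file. But patients are listed before they start, with their expected treatment day, and results remain linkable through the pseudonym (section 6.3). Provided the laboratory system holds collection dates, which is assumed here, the team can establish which samples were pre-dose. Assay development is a separate aim (item 2 of section 3.2), so its value does not hang on item 3.

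The claim that the objective cannot test its rationale is also an inference from section 5.1, and it weakens if any samples are on-treatment. The exclusion of known endocrine disease does not rule out undiagnosed thyroid dysfunction at baseline, so the thyroid reason is not purely a later-time one.

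**Conclusion.** The observation is accurate, but no change to the plan follows. The readable text implies a pre-dose sample, and most of the background reasons for malondialdehyde concern later states. A pre-dose result therefore speaks to baseline risk and not to a rise caused by treatment or present at the irAE. Baseline risk is what section 3.3 asks about, and the planned comparison is valid for it. A null result supports leaving the marker out of a pre-therapy algorithm; it should not be written up as refuting the mechanism. That is a matter for the discussion of results.

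The missing window is a gap that analysts would fill sensibly, with little effect on the error rate (5 to 6% under the hypothetical 2% contamination). Adding an on-treatment sample is a trade-off the team may fairly decline: up to 120 more measurements and stored aliquots, for a comparison that still misses the at-event reasons.

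The conclusion rests on the pre-dose reading of section 5.1, which the flow chart may confirm or alter. The power figures rest on assumed differences of 0.6 and 0.8 SD, assumed shares present before the dose, and an assumed t-test.

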5.2 PATIENT CONSENT

Enrolment onto this study required patient consent; this will be achieved by telephone. Samples will not be tested unless patient consent has been obtained. Once eligible patients have been selected and their samples have been stored a member of the research team will contact the patient as per BIO-CHECKPOINT Telephone Consent Script, version 1.0. The research team will offer to send the patient the PLS BIO-CHECKPOINT adults version 1.0 information leaflet and arrange to call back at a suitable time to take consent recorded via the BIO-CHECKPOINT version 1.0 Consent Form.

Participants expressing an interest in the study will have their eligibility assessed, receive a PIS and will have adequate time to read this information. The information will also be presented to them verbally to ensure they understand. If they would like to, they will be able to talk to relevant health care professionals or family members about involvement in the study and will have the opportunity to ask any questions they may have before consent is taken. If the patient does not consent to the study the samples will be destroyed and not tested.

BIO-CHECKPOINT

5.3 SAMPLE ANALYSIS

Residual serum and plasma that will be anonymised will be defrosted and run at the Blood Sciences laboratory in Portsmouth.

Blood tests will be run on UKAS ISO15189 accredited blood analysed by stated registered Clinical Scientists and Biomedical Scientists. Malondialdehyde levels will be assessed via isotope dilution mass spectrometry method or an ELISA kit in the event of method validation failure. The method will be fully validated and installed at Portsmouth Pathology laboratories. It is not anticipated that there will be any sample remaining at the end of the analysis procedure. Any sample that remains at the end of the analysis procedure will be destroyed as per standard NHS Pathology Department guidelines.

5.4 REPORTING OF ACTIONABLE RESULTS

Critically abnormal results may be produced during this study. To avoid moral dilemma of if to report results that the clinician did not request the following mitigating factors have been put into place. Samples will be labelled and booked in under a pseudonym and only the lead researcher will have access to the key and relevant patient identifiers. Samples will be batched and run once a post collection, making these results historic values. Results will not be clinically correlated to patient outcomes until May 2025 meaning outcomes of any abnormal results would have likely presented by this point. Clinicians will not see or be able to look up the study's results.

6. DATA PROCESSING

6.1 DATA TRANSFER AND STORAGE

Results will be anonymised under a pseudonym/reference on the laboratory information management system (APEX). This is a password protected system that only authorised personnel can access on password protected Trust accounts, which are also password protected. The patients' clinicians will not be able to see these results or link them to their patients. Only those on the research team will be able to de-anonymise the data. Results will be stored on APEX during the study. Post study completion the results will be extracted from APEX into a password protected excel sheet. Results and patient identifying data will not be sent outside of the Trust.

6.2 SOURCE DATA

Laboratory results, CVs, delegation logs will be deemed source data.

6.3 DATA CONFIDENTIALITY

BIO-CHECKPOINT

The central research team Portsmouth Pathology i.e., [name] and [name] will have access to patient data and anonymised result data. This data will be stored securely on password protected computers at the NHS Blood Sciences laboratory in Portsmouth. Patient identifiable data will not be stored outside of the Trust computers. Linkage of test results to personal identifiable information will only be possible through the pseudonym/reference. Linkage will only be carried out by [name]. Statistics will be carried out by [name] as this study is part of their Doctorate in Clinical Science awarded by the University of Manchester. Statistics will be carried out using R on a password protected personal computer. Data for statistics will not contain patient identifiable data i.e., first name, surname, date of birth, hospital number, NHS number, post code, etc. Data will be stored for 1 year post completion of the study before being archived or deleted in line with the sponsors' policy.

6.4 DATA ARCHIVING

At the end of the study, archiving will be carried out in accordance with sponsor protocols and, where relevant, local site governance requirements.

7.0 SAMPLE SIZE

All adult oncology patients at Queen Alexandra Hospital who are prescribed FDA approved ICPI for the first time, providing they don't meet the exclusion criteria will be recruited. The sample size is expected to be around 120 patients, based on ICPI patient Portsmouth Hospital University Trust data from 2022. It is estimated that around 40-66% of patients on ICPI will have an irAE based on the literature.

Assuming an incidence rate of 40% for irAE, this study would require at least a sample size of 47 individuals assuming a significance criterion of $\alpha=0.05$ and power =80.

The study will run for 18 months and hopes to obtain at least a sample size of 47 individuals, depending on how many patients are referred for ICPI therapy. The study will end before 18 months if we recruit 150 patients before the end date.

The period of testing was decided upon discussion with the Oncology department, based on ICPI prescriptions provided by the pharmacy department.

8.0 STUDY MANAGEMENT

The chief investigator and lead researcher are responsible for the day-to-day operation of the study. Management support for this study will be provided by the Research and development department at Portsmouth Hospital University Trust.

BIO-CHECKPOINT

9.0 HEALTH RELATED FINDINGS

Samples will be stored and tested under a pseudonym/reference one month post initial collection. Clinicians will not have access to these results and those testing the samples will not know who the sample belongs to. Results will not be linked to the patients' records until completion of the data collection period i.e., May 2025.

10.0 END OF STUDY

The study will finish 6 months post the final analysis of samples has been undertaken.

11.0 FUNDING

This study will be funded by the Higher Specialist Scientist Training (HSST) program via the National School of Healthcare Science and by the Royal College of Pathologists Fellowship Research Start-up Grant.

12.0 MONITORING AND INDEMNITY

Monitoring of this study will ensure compliance with Good Clinical Practice. The Investigator (s) will permit monitoring, audits, REC review and regulatory inspections by providing the Sponsor, Regulates and REC direct access to source data and other appropriate documents (e.g., study data collection forms).

NHS Indemnity will apply.

13.0 IMPORTANCE AND POTENTIAL BENEFIT

This study is aiming to act as service improvement collaboration between Oncology and Pathology services at Portsmouth Hospital University trust. To help highlight which blood tests help to highlight ICPI at risk of developing irAE. On the basis of the results produced we aim to produce a blood test panel that can be ordered on our blood requesting software (ICE) for all ICPI patients. This will help to increase consistency in blood test requesting and diagnosis of ICPI irAE faster.

This study will also further the progression of [name]'s career and professional development. This will allow development of mass-spectrometry skills, data processing and analysis as well as journal publications. Completion of this project will also feed in to [name]'s Royal College of Pathologists exams for her fellowship.

BIO-CHECKPOINT

